Pre-exposure prophylaxis (PrEP) is a key biomedical HIV prevention strategy that can significantly reduce HIV incidence in real-world settings. Yet globally, PrEP introduction and scale up have been slow. PrEP is typically integrated into existing health systems through a hit-or-miss process that is rarely studied, leaving a gap in understanding of implementation processes, and how sociopolitical and cultural contexts influence implementation. A scientific study of the process of introduction and implementation of PrEP in a specific international health system has the potential to produce actionable knowledge, and more efficient and effective implementation that will both reduce HIV incidence and costs within the existing system and accelerate access to effective prevention in similar health systems. PrEP implementation in the US and globally has taught us that clinical guidance is necessary but not sufficient for large scale implementation. Effective implementation has multiple components. Health systems must 1) build awareness and generate demand; 2) identify potential

beneficiaries; 3) offer and link people to services; 4) get pills to those who need them; and 5) support users to adhere both to pills and to regular check-ups. These five components comprise the PrEP Care Continuum (Kelly et al., 2015; Nunn et al., 2017). Studies are testing strategies for each of these components: for example, comparing methods for screening (Kelly et al., 2015), evaluating the impact of same-day initiation (Wendel, 2017) and testing different retention strategies (Amico & Stirratt, 2014; Holtzman et al, 2015; Fuchs et al., 2018). While knowledge generated in each of these studies is critical, not one is holistic enough to inform planning for large, state-run health systems seeking to integrate PrEP into services. What is needed are protocols to detail how to implement what the clinical protocol specifies.

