The overall study uses a stepped-wedge design to understand PrEP implementation at eight study sites in Yunnan, China. Each study site will go through four study periods. Sites will start with a six-month pre-baseline period, where PrEP is not offered but HIV prevention utilization data will be collected among MSM client population. HIV prevention utilization data will be captured by the PrEP M&E data system created by Yunnan CDC. Examples of indicators to be collected include number and frequency of HIV and STI tests, diagnoses, and treatment status. These metrics will be collected throughout all study periods. Each site will then have a different length of Baseline Period of standard PrEP implementation followed by a one-year Experiment Period with enhanced PrEP implementation.

The study procedures involve audio recording of research subjects. All study procedures will be performed at eight study sites by research staff who have completed human subject protection training after obtaining informed consent from participants. This study will not use previously collected biospecimens, data or records. Detailed study procedures are listed below:

Audio and/or video recording of research subjects: This study will conduct in-depth interviews with (1) MSM clients, and (2) program staff to understand their experience with PrEP implementation. Interview guides are submitted in English only as these are documents to guide the English-Chinese bilingual interviewers. Therefore, no Chinese version of the interview guide is attached. We will audio-record interviews with participants who provide permission for recording. Audio-recording is a very widely used technique in qualitative research. It allows researchers to fully engage and concentrate on the interview rather than writing notes, which may be a distraction for both the

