interviewer and the participants. Audio-recording will help researchers keep accurate records of qualitative data and capture non-verbal expressions during the interview. Informed consent will be obtained before any study procedures are initiated. During the consent process, the interviewer will ask participant's permission for audio-recording. For detailed process of obtaining consent, please see section "Informed Consent Process". After informed consent is obtained, the interviewer will announce that the interview will begin and turn on audiorecording equipment. The interviewer will begin the interview by noting the time, date, and unique ID number for the interview. S/he will proceed to conduct the interview guided by the interview guides. The interview will be in-person or remotely one-on-one and is expected to last 45 to 60 minutes. All data will be confidential and protected. Compensation of 100 Yuan (approximately USD \$16) will be provided upon completion of the interview. De-identified data will be sent to contractors external to Columbia University to support data analysis.

Study Design

B-HAPPY is a multisite randomized stepped-wedge trial to compare the effectiveness of two implementation strategy bundles: 1) Standard Implementation: comprising the strategies that the Yunnan CDC would usually use to introduce HIV prevention innovations in the absence of the proposed study; and 2) Enhanced Implementation: standard implementation enhanced by a SIC-guided approach to plan and implement PrEP. Eight sites will receive identical Standard Implementation during a six-month baseline period; additional strategies will be introduced to blocks of 2 sites in six-month increments. Importantly, the role of the SIC will shift between Baseline when

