All data will be in electronic format and we will not have any hard copy of study data. In general, we will use Secure Sockets Layer (SSL) encryption to securely transfer the study data that are in electronic format. We will store study data on password-protected, encrypted computers, and will restrict access to the data to key study personnel.

This study will analyze data from five different sources. Here is a detailed description of how we will ensure confidentiality and safely stored data from five different sources:

1. SIC and COINS data

Description: The PrEP-SIC data includes a log of implementation activities completed by each site along with the dates of activity completion (e.g.: date written PrEP implementation plan completed, date first PrEP user retained in care for six months). The COINS tool assesses direct and indirect expenses, including the number of hours per role expected in completing each implementation activity listed in the SIC. SIC and COINS data will be collected by our Yunnan-based research coordinator through phone call and in-person site visits at two to four-week intervals and entered

into the SIC website. SIC and COINS tool measures implementation process and does NOT contain personal identifiable information (PII) or protected health information (PHI).

2. PrEP M&E data

Description: Yunnan CDC (our primary collaborator in China and a subaward recipient on this grant) is upgrading their HIV prevention monitoring and evaluation (M&E) system to incorporate PrEP service delivery indicators. We expect this PrEP M&E data system to start working in May 2020, and it will document data including routine HIV utilization, PrEP service delivery and process measures for all facilities involved in PrEP implementation across the province and including at our study site. Yunnan CDC staff will extract data and aggregated at site level (e.g. number of HIV testing done per site, percentage of MSM clients receiving sexual health needs assessment, number of PrEP initiations). Only this site-level, aggregated data will be shared with the B-HAPPY study team.

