Traditional designs—whether client-randomized or site-randomized—were not viable due to statistical power, contamination risk, and the dual focus on intervention and implementation outcomes. For instance, randomizing clients would risk contamination within sites, and randomizing sites would drastically restrict power. This

is addressed by the proposed stepped-wedge design,²⁵⁻²⁷ with all sites participating in a baseline period (Standard Implementation), experiment period (Enhanced Implementation), and post-experiment period (Observation). Blocks of sites are randomized to the *timing* of the experiment period. Because intervention condition *changes over time*, the intervention effects reflect within-block changes (e.g., between the Enhanced and Standard periods). The design is highly flexible and maximizes power, and the proposed analyses straightforwardly accommodate different data structures for client-services outcomes (Aim 1) and implementation process outcomes (Aim 2), clients that span periods, and outcomes that are both research- and site-collected.

Data structure. For Aim 1, the *client-services outcomes* are structured with repeated visits (level-1) that are nested within clients (level-2) who are nested within periods (level-3) that are nested within sites (level-4). However, for analysis, the outcomes will reflect a single status for each client (e.g., initiation of PrEP), reducing the data to a three-level structure. For Aim 2, the *implementation process outcomes* are structured with three repeated measurements (i.e., across the baseline, enhanced, and observation periods; level-1) that are nested within sites (level-2). In each case, the small number of sites will be addressed. Of note, across aims, supplementary time-to-event analyses^{28, 29} (e.g., the effect of Standard Implementation on time to client awareness) are possible by reformulating the data to client- and site-period structures. Likewise, clients will be associated with the period in which the outcome status is finalized.

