Model building, estimation, and significance testing. The nested data structures will be evaluated using mixed-effects regression models, but with 8 sites, specialized methods are required to estimate and validate the effects.^{29,30} Model estimation will utilize Bayesian Markov chain Monte Carlo (MCMC) methods.²⁷ With this approach, the results are based on a large number of replications, providing an empirically-based sampling distribution—rather than a single point estimate—for each model parameter (e.g., the effect of Enhanced Implementation). Further, the conclusions will be validated using a frequentist, fixed effects approach (i.e., dummy-coded indicators) to control for site effects.³¹ To test for within-block changes across the three periods, two dummy-coded indicators will be included to differentiate the Enhanced and Observation periods from the reference Standard period. Continuous, dichotomous, and ordered categorical outcomes will be evaluated according to Gaussian, binomial, and ordinal distributions. To evaluate the magnitude and precision of effects, 95% CIs will be computed, along with odds ratios (ORs) for non-linear outcomes. The Bayesian MCMC models will be implemented in MLwiN,²⁷ and single-level regression models will be implemented in R.³²

Evaluation of Specific Aim 1: To evaluate whether the addition of SIC-guided PrEP delivery (Enhanced Implementation) to standard health system PrEP delivery improves services outcomes, including: awareness, screening, offer, initiation, and continuation at 6 months. Although the outcomes are repeatedly monitored, each reflects a client-level status. The three-level mixed-effects regression model, with clients (level-1) within periods (level-2) within sites (level-3), will include control variables for client characteristics (e.g. age, partnership status, ethnicity [Han vs other], sexual identity) and site characteristics (e.g. staffing, collaboration history between VCT and

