STI clinics, institutional leadership, localized epidemiology), along with indicators for study periods. Additionally, to control for temporal effects—natural improvements in PrEP implementation over time—for each client, the models will control for the time of study entry using linear and quadratic polynomials for the number of months from the start of the Standard period. With a single outcome status for each client, this controls each client's outcomes for the timing of participating during the site's PrEP implementation process. The results will indicate the average within-block change from Standard to Enhanced in the log-odds of awareness, screening, offer, initiation, and continuation. Likewise, to determine whether the effects are maintained, outcomes from the Sustainment period will be compared to the Standard and Enhanced periods.

Statistical power for Aim 1. Multilevel power analysis typically assumes interventions are at the level of individuals or groups. However, here, the intervention is time-varying. As such, power for the primary client-services level outcomes was estimated using a multi-step approach recommended by Hox³³:

First, the *total sample* of observations was computed. For client-services level PrEP outcomes (ie, awareness, screening, offer, initiations, continuation), the sample size calculation reflects the size of the site client population and the availability of donated TDF/FTC (minimum of 1064 PrEP initiators). We anticipate ~2600 MSM clients per site per year and estimate ~133 PrEP initiators per site. However, this sample size is nested, introducing dependency and decreasing the level of statistical power.

Second, to penalize the total sample for nesting, the design effect formula is reorganized (i.e. $n_{\text{eff}} = n/[1+\{n_{\text{clus}}-1\}]$) to provide the effective sample size of independent observations. Using a conservative nesting effect (i.e. =0.25 for phases/sites), the

observations provide statistical power equivalent to 32 independent observations.

Despite the large number of MSM clients each year, the effective sample reaches an upper limit of 32 due to (a) the small number of sites and (b) the large cluster size per site. However, the large cluster provides high reliability for estimated level-2 effects.

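### Six-month continuation: the plan does not say when a status becomes final or how a window that crosses a switch is labelled, so the Standard-to-Enhanced contrast can be biased in either direction

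*Combined protocol and SAP*

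**What the plan says.** The SAP's Data structure paragraph reduces each Aim 1 outcome to one status per client. After a sentence on supplementary time-to-event analyses it adds: "Likewise, clients will be associated with the period in which the outcome status is finalized". No other sentence assigns clients to periods, and the date of finalization is not defined. The opening SAP paragraph says the analyses can handle "clients that span periods, and outcomes that are both research- and site-collected", but gives no exclusion, transition window or sensitivity analysis for them.

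Under Evaluation of Specific Aim 1, continuation at six months is one of five outcomes: "Although the outcomes are repeatedly monitored, each reflects a client-level status". The model compares Enhanced and Observation indicators with Standard, and "the models will control for the time of study entry using linear and quadratic polynomials", counted in months from the start of Standard.

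On the schedule, Study Design gives a six-month baseline, after which "additional strategies will be introduced to blocks of 2 sites in six-month increments". Study Procedures says that Baseline length differs by site, "followed by a one-year Experiment Period with enhanced PrEP implementation". The length of the Observation period is not stated.

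**The concern.** Awareness or initiation happens at a point in time. Continuation takes six months to observe, and six months is also the step length. Many clients who start PrEP under Standard will therefore be observed partly or mainly under Enhanced. How they are labelled decides what the contrast measures, and the SAP's wording allows two rules.

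- **Month-6 reading.** Every starter's status is final six months after starting. Outcomes that began under Standard are then counted as Enhanced.
- **Stop-date reading.** A client who stops is final on the stop date, and a client who continues is final at month 6. The label then depends on the outcome: near a switch, failures stay in Standard and successes move to Enhanced.

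The first can hide a real benefit and the second can create a false one. The model's time term is keyed to study entry while the label is keyed to a later date, so the time term cannot be relied on to correct the labels.

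**Working it through.** **Inputs.** Four blocks of two sites. Standard lasts 6, 12, 18 and 24 months (inferred from Study Design and Study Procedures), Enhanced 12 months, and the outcome window is 6 months. The effect is the plan's OR of 3.3. Assumed, because the documents do not say: even starts, study entry at PrEP start, no secular trend, effect kept in Observation, and four possible Observation schedules.

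**1. The plan's effect size.** Centred on 50%, √3.3 = 1.817 and 1.817/2.817 = 64.5%, against 35.5%. The difference is 29 points, as the plan states. These rates come from a generic power effect; the plan gives no continuation rate.

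**2. Windows that cross the switch.** Starts in the last six Standard months are 6/6, 6/12, 6/18 and 6/24 of the four blocks (100%, 50%, 33%, 25%). Pooled, this is 24/60 = 40%. With a linear ramp it is (36+108+180+252)/(36+144+324+576) = 576/1080 = 53%. With sites weighted equally it is (100+50+33+25)/4 = 52%. With front-loaded starts it is 31-36%. Under month-6 labels, 24 of the 48 Enhanced-labelled start-months began under Standard, and block 1 has no Standard-labelled outcome.

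**3. Month-6 reading, without entry-month terms.**
- Effect set at start: Enhanced-labelled rate = 35.5 + 29/2 = 50.0%. OR = (0.500/0.500)/(0.355/0.645) = 1.82.
- Effect building evenly over the window: crossing starts average half the effect, so the rate = 35.5 + (14.5+29)/2 = 57.25%. OR = (0.5725/0.4275)/(0.355/0.645) = 2.43.
- No effect: OR = 1.00.

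**4. Stop-date reading, no true effect, 80% continuation, even stop times, without entry-month terms.** In start-month units:
- Standard-labelled: 0.8×36 = 28.8 continuers; 0.2×36 + 0.2×24×½ = 9.6 stoppers; ratio 3.0.
- Enhanced-labelled: 0.8×48 = 38.4 continuers; 2.4 + 4.8 + 2.4 = 9.6 stoppers; ratio 4.0.
- Pooled OR = 4.0/3.0 = 1.33, or about 1.4 with block effects. In block 1 every Standard-labelled client is a stopper.

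**5. Adding linear and quadratic entry month.** These are large-sample fits of the SAP's fixed-effects check model (block effects, Enhanced and Observation indicators). The true OR is 3.3 unless marked null. Columns are Observation lengths in months; the last two assume a common end date.

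| Label | Effect | 6 in all blocks | 12 in all blocks | 24/18/12/6 | 30/24/18/12 |
|---|---|---|---|---|---|
| Month 6 | set at start | 0.82 | 0.99 | 1.26 | 1.34 |
| Month 6 | builds up | 1.43 | 1.62 | 1.89 | 1.97 |
| Month 6 | null | 1.00 | 1.00 | 1.00 | 1.00 |
| Stop date | null, 80% | 9.62 | 7.87 | 4.23 | 3.35 |
| Start date | set at start | 3.30 | 3.30 | 3.30 | 3.30 |
| Start date | builds up | 1.54 | 1.54 | 1.69 | 1.82 |
| Whole window in one period | either | 3.30 | 3.30 | 3.30 | 3.30 |

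Under month-6 labels the Enhanced indicator switches on six months too early on the entry-month scale. The polynomial absorbs part of the real step, so the month terms lower the OR further. Using the share of the six months spent under Enhanced as the exposure gives 3.3 if the effect builds up and 2.6-2.8 if it is set at start.

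**The case against.** **Direction.** A reader might infer that the rule simply attenuates the effect. The documents do not support that. The month-6 reading is arguably the more natural: the outcome is one status per client, and the SIC log records the "date first PrEP user retained in care for six months". But that log item is a site milestone for one retained client and does not say when a stopper's status is final. A single client-level status fits both readings.

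**Scope.** The sentence follows the one on time-to-event analyses and may govern only those. The bias sizes would then belong to no stated main-model rule, and what remains is the absence of one. The SAP needs text either way.

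**Size.** The 40% needs even starts and a fixed month-6 date, and even accrual is not documented. The lowest ORs come from the labels and the month terms together; labels alone give 1.8 or 2.4. If the effect is lost in Observation, the month-6 results are 0.8-2.2 (set at start) and 1.6-2.6 (building up), and can reach 3.8 if Enhanced also triples starts. These qualifications stand, and the sizes are conditional.

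**Remedy.** It is tempting to relabel everyone by PrEP start date. That works only if the effect is fixed at initiation. The rationale says systems must "support users to adhere both to pills and to regular check-ups", which suggests that support also acts during follow-up. In that case start-labelling gives 1.5-1.8, no real improvement on 1.4-2.0.

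**Coherence.** Labelling when status is ascertained suits the monthly Five-80 benchmarks. It does not suit a contrast meant to attribute the outcome to the implementation condition.

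**Conclusion.** The concern holds for six-month continuation only; nothing here shows bias in awareness, screening, offer or initiation. The assignment rule is undefined, possibly absent from the main model, and gives a wrong estimate on either reading. With month-6 finalization there is no bias under the null, but a true OR of 3.3 reads about 1.8 or 2.4 without the entry-month terms and about 0.8-1.3 or 1.4-2.0 with them. With stop-date finalization, no effect reads as a benefit: about 1.4 without the month terms and 3.4-9.6 with them.

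The sizes rest on the inferred schedule and the assumptions listed with the inputs. They come from the fixed-effects check model; the primary Bayesian model was not run. This should be fixed, with medium confidence in the sizes.

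**What to change.** For continuation only:

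1. Score status at month 6 for every starter with six months of possible follow-up who remains PrEP-eligible, whenever a stop was recorded. The label then never depends on the outcome.
2. Estimate the Standard-to-Enhanced contrast from starters whose whole six-month window lies within one period. If that is too thin, use all starters, with the share of the six months spent under Enhanced as the exposure.
3. Report labelling by PrEP start date as a sensitivity analysis, described as the effect of starting under Enhanced. It should not be the sole replacement.
4. State whether the existing sentence applies to the main model. Leave the other four outcomes unchanged.

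**Cost.** SAP wording and a data specification. The Confidentiality section says that only site-level aggregates reach the study team, so the Yunnan CDC extract must be tabulated by site and PrEP-start month (starters, still eligible at month 6, continuing at month 6).

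The whole-window analysis leaves block 1 with no Standard data. It keeps 0+6+12+18 = 36 of 60 Standard and 4×6 = 24 of 48 Enhanced start-months. With 1064 starters its standard error for the log OR is about 1.4-1.9 times that of start-labelling. It also leans more on the month terms: with an assumed saturating trend of 1 logit × (1 − exp(−t/6)), which the quadratic misses, a null reads 0.87-0.94 and a true 3.3 reads 2.9-3.1.

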Implementation outcomes. For Aim 2, with the focus on implementation process outcomes (rather than client services outcomes), the data are structured with three periods (level-1) within sites (level-2). The outcomes include the proportion of implementation activities completed, duration of activity completion, maximum implementation stage reached, and benchmarks on the Five-80s (3 consecutive months for implementation, 6 consecutive months for sustainment). The model will include key client and site characteristics, and dummy-coded indicators to differentiate the three periods. The results will indicate the difference between Enhanced and Standard in the level of each implementation outcome. As with Aim 1, the conclusions will be validated based on single-level models with fixed-effect control variables for site differences. Likewise, with the focus on achieving implementation process benchmarks, the model

will be extended to a time-to-event framework,²⁹ testing for differences between Enhanced and Standard in the time required to achieve benchmarks (adjusted for the duration of the Standard period). With the focus on implementation process outcomes, power for this aim is inherently limited. Results will focus on estimates of 95% CIs for the effect of Enhanced Implementation.

Attrition & Missing Data. Following intention-to-treat principles, sites will be retained in research measurement independently of participation in Enhanced Implementation.³⁴ Highly successful tracking and retention protocols will minimize missing data. However, some data will inevitably be missing. To address this, assumptions will be evaluated, and informed by the results, one of several approaches will be used³⁵: i) For a small proportion of missing data with evidence of Missing at Random (MAR), the data will be analyzed using the estimation procedures described above. ii) For a non-trivial amount of missing data and evidence of MAR, multiple imputation for repeated measurements will be used.³⁶ iii) For a non-random missing data mechanism, pattern mixture models will be used to identify and control the effect of the non-random mechanism.^{37, 38}

Data Analysis

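### The frequentist check of Aim 1 omits the period-within-site level of the primary model, so its 95% CIs are too narrow if sites change differently between periods

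*Combined protocol and SAP*

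**What the plan says.** The SAP section on Specific Aim 1 defines the primary model: "The three-level mixed-effects regression model, with clients (level-1) within periods (level-2) within sites (level-3". It is fitted by Bayesian MCMC.

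The section on model building, estimation and significance testing then adds the check: "the conclusions will be validated using a frequentist, fixed effects approach (i.e., dummy-coded indicators) to control for site effects". Its software sentence says "single-level regression models will be implemented in R". The section on implementation outcomes confirms that this describes Aim 1: "As with Aim 1, the conclusions will be validated based on single-level models with fixed-effect control variables for site differences".

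The period terms are the same for every site: "two dummy-coded indicators will be included to differentiate the Enhanced and Observation periods from the reference Standard period". So are the time terms, which are "linear and quadratic polynomials for the number of months from the start of the Standard period". Client and site characteristics are added as covariates. Neither a site-by-period term nor a cluster-robust or small-sample variance is stated for the check.

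On volume, the power section says "We anticipate ~2600 MSM clients per site per year and estimate ~133 PrEP initiators per site". On dependence, it says "Using a conservative nesting effect (i.e. =0.25 for phases/sites", without dividing that value between sites and phases within sites.

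**The concern.** The Aim 1 effect is a within-site change from Standard to Enhanced. A valid interval must therefore carry the variation between sites in that change. The primary model has a level for it. In the check, site dummies remove only the stable differences between sites. Drift shared by all sites that follows the month terms is also absorbed and does no harm. What remains is site-specific change between periods, and a single-level model with model-based standard errors treats clients who share such a change as independent.

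What is at stake is false reassurance: a Bayesian conclusion could be called validated by an interval that is too short, or an apparent disagreement in precision could be an artefact. The exposure is greatest for outcomes measured on all MSM clients (awareness, screening). Offer, and initiation among linked clients, have volumes that the documents do not give.

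**Working it through.** **The plan's own figure.** The effective sample size of 32 reproduces with n/[1 + (m − 1)ρ] and ρ = 0.25: 1064/(1 + 132 × 0.25) = 31.3 for initiators, 20,800/(1 + 2599 × 0.25) = 31.96 for all clients in a year, with limit 8/0.25 = 32. Sites are the clusters here, so 0.25 does not supply the site-by-period part.

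**Inputs from the documents.** 8 sites in blocks of 2, six-month steps, Enhanced lasting 12 months; hence Standard lasts 6, 12, 18 or 24 months by block. About 2600 clients per site per year, and 133 initiators per site (1064/8).

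**Assumptions.** 42 months in all (7 steps; the length of Observation is not given), outcome near 50%, no covariates, two-sided 5%. Site-by-period ICC of 0, 0.005, 0.01 or 0.05 on the logit scale, so the variance is v = ICC/(1 − ICC) × π²/3 = 0, 0.0165, 0.0332 or 0.173. The last three ICCs are 2%, 4% and 20% of 0.25.

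**Formula.** For a logistic model with site dummies, the two period indicators and linear and quadratic months, this layout gives, with n new clients per site-step:

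- model-based SE of the Enhanced log-odds ratio = 1.034/√n;
- true variance = SE² + 0.303v (both constants come from the design matrix);
- type I error = 2Φ(−1.96 × SE/true SD).

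Example, n = 300 and ICC 0.01: SE = 1.034/√300 = 0.0597; true SD = √(0.00356 + 0.303 × 0.0332) = 0.117; ratio 1.96; error 2Φ(−1.00) = 32%.

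| New clients per site-step | ICC 0 | 0.005 | 0.01 | 0.05 |
|---|---|---|---|---|
| 19 | 5% | 6% | 7% | 16% |
| 38 | 5% | 7% | 9% | 25% |
| 100 | 5% | 11% | 16% | 42% |
| 300 | 5% | 21% | 32% | 62% |
| 1300 | 5% | 46% | 59% | 81% |

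**Reading the volumes.** 19 is 133/7. It derives from a total of 1064 that the power section calls a minimum, so it is not a ceiling; 38 shows twice that volume. 1300 is half of 2600 and is an upper end: with one status per client it means 1300 × 7 × 8 = 72,800 different men, against 80,000 PrEP-eligible MSM estimated for the province, and the 2600 may include returning clients. 100 and 300 are illustrative.

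**Simulation.** Binomial simulations of this layout at 300 per step and ICC 0.01 give 27 to 30%, slightly below the analytic 32%; in one of them the mean SE was 0.062 against a true SD of 0.113 (ratio 1.82). A separate simulation with six months of Observation, at 2600 clients per site per year, gave coverage of 94.7% at ICC 0, 50.4% at 0.01 and 25.3% at 0.05. With only shared quadratic drift, the check as planned rejected 3.4 to 5.2%.

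**Other settings** at 300 per step and ICC 0.01: 24% if the outcome is near 80%; about 27% with 6 steps and 35% with 8.

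**The repair.** In simulation, site-clustered CR2 with Satterthwaite degrees of freedom rejected 4.0 to 5.5% at 19, 300 and 1300 per step and at every ICC tried, whether site shocks lasted a whole period or varied by step. With unequal site volumes it rejected 5.6 to 6.1%.

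**The case against.** The plan is silent on a clustered variance; it does not rule one out. The data-structure section promises to deal with the small number of sites, and the model-building section says that special methods are needed both to estimate and to validate, citing a source on very few clusters. That softens the point. For the check, however, the only device named is the site dummies, and these do not reach the period level.

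The size is conditional throughout. The variance, the volume per step and the length of Observation are assumed. The planned covariates are left out, and site characteristics that vary over time could absorb part of the site-by-period variance. Awareness is also asked in an anonymous exit checklist with no stated completion rate. All of this stands, and it makes the table a sensitivity range.

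The check is secondary, has no decision rule, and does control for site effects as it says. That stands too and limits the severity.

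Four stronger readings are tempting and are not supported:

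- That 0.25 is the site-by-period correlation, which would make the check almost useless. The 32 follows from 0.25 with sites as clusters, and the value is not split.
- That the Aim 1 conclusions are invalid. The primary model carries the period level.
- That continuation is safe because initiator volume is capped at 19 per step. The underlying total is a minimum.
- That Aim 2 fails in the same way. There, period is the lowest level, so no clients within a site-period are treated as independent.

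**Conclusion.** The omission is certain from the text: the check has no period-within-site level and states no variance that would make up for it. The consequence is conditional. If sites change differently between periods, the check's 95% CIs are too narrow; if that variance is zero, they are correct.

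The possible size runs from nothing to severe. For outcomes on all clients, an ICC of only 0.005 doubles the nominal 5% error at 100 clients per site-step and quadruples it at 300. At 19 to 38 initiators per step the error stays at 6 to 9% up to ICC 0.01 and reaches 16 to 25% at 0.05. None of these figures is an estimate for this trial. The change should be made because the check is meant to validate conclusions and the repair is cheap.

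**What to change.** Keep the planned single-level check and its point estimate. Replace the model-based standard error by a cluster-robust variance clustered on site with the CR2 small-sample correction, and give Satterthwaite t-based 95% CIs for all five Aim 1 outcomes. The degrees of freedom are about 6.5 in the layout above without covariates and 5.4 in the unequal-volume simulation; compute them from the fitted model. Also report the site-by-period variance from the primary Bayesian model, so that readers can see whether the condition applies.

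The section on confidentiality of study data says that only site-level aggregates from the M&E system reach the study team. If that is all there is for an outcome, the same variance can be applied to counts, without client covariates.

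The cost is SAP wording and one variance call in R, plus wider intervals. In simulation at 300 per step and ICC 0.01, the OR is multiplied or divided by exp(2.40 × 0.112) = 1.31 instead of exp(1.96 × 0.062) = 1.13. If the variance is zero, the factor is 1.15 instead of 1.13. At 19 initiators per step it is 2.14 instead of 1.62 at ICC 0.05, and 1.75 instead of 1.61 at zero variance. Power at that volume for the plan's OR of 3.3 is 95% at ICC 0.01 and 82% at 0.05; for OR 2.0 it is 60% and 41%.

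The choice of CR2 is partly a preference. A random intercept per site-by-period is slightly more precise, but in simulation rejected 7 to 14% of true nulls at 300 to 1300 per step when site shocks varied by six-month step. An analysis of the 24 site-period rows rejected 4.4 to 6.4%, with an SE 2.6 to 3.6 times that of the CR2 check. The SAP should name one method.
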